### **Dosing Delays for General and Immune-Related Adverse Events**

Algorithms in tables which follow and Appendix 5 should be consulted for specific immune-related AEs and followed preferentially rather than this general guideline.

Grade of Event	Management/Next Dose for Nivolumab
≤ Grade 1	No change in dose
Grade 2	Hold until ≤ Grade 1 Resume at same dose schedule when toxicity ≤ Grade 1
Grade 3	Hold* until ≤ Grade 2 Resume at same dose schedule when toxicity ≤ Grade 2
Grade 4	Off protocol therapy

\*Patients requiring a delay of > 28 days should go off protocol therapy

### **Please note nivolumab therapy will not be delayed for the following:**

- Grade 2 weight loss;
- Grade 2 or 3 nausea that in the opinion of the investigator is related to cisplatin;
- Grade 3 radiation dermatitis;
- Any Grade 2-3 mucositis, dysphasia, or pharyngolaryngeal pain that in the opinion of the treating physician is related to radiation therapy for head and neck cancer;
- Grade 2 hypokalemia or hypomagnesemia that in the opinion of the investigator is related to cisplatin;
- Grade 2 or greater hearing impairment that in the opinion of the treating physician is related to cisplatin;
- Grade 3 or 4 isolated lymphopenia;
- Grade 3 isolated anemia if, in the opinion of the treating physician, the anemia is not related to the study drug (e.g. related to chronic disease, iron deficiency, radiotherapy).

#### **Skin Rash and Oral Lesions**

≤ Grade 1

#### **Management/Next Dose for Nivolumab**

No change in dose\*

Grade 2	No change in dose; see guidelines for management in Appendix 5.
Grade 3	Hold* until $\leq$ Grade 1; see guidelines for management in Appendix 5. Resume at same level at investigator discretion
Grade 4	Off protocol therapy

\*Patients with purpuric or bullous lesions must be evaluated for vasculitis, Steven-Johnson syndrome, TEN, and autoimmune bullous disease including oral lesions of bullous pemphigus/pemphagoid. Pruritus may occur with or without skin rash and should be treated symptomatically if there is no associated liver or GI toxicity. Note skin rash typically occurs early and may be followed by additional events particularly during steroids tapering.

Liver Function	Management/Next Dose for Nivolumab
AST/ALT/T. Bili *	
$\leq$ Grade 1	No change.
Grade 2	Hold until UNL or baseline. Resume at same dose schedule; see guidelines for management in Appendix 5.
Grade 3	Off protocol therapy; see guidelines for management in Appendix 5.
Grade 4	Off protocol therapy see guidelines for management in Appendix 5.
Continued treatment of active immune-mediated hepatitis may exacerbate ongoing inflammation. Holding drug to evaluate LFT changes and early treatment are recommended. LFT changes may occur during steroid tapers from other events and may occur together with other GI events including cholecystitis/pancreatitis.	

Renal Function	Management/Next Dose for Nivolumab
Serum Creatinine	
$\leq$ Grade 1	Continue treatment.
Grade 2	Hold until UNL or baseline. Resume at same dose schedule; see guidelines for management in Appendix 5.
Grade 3	Hold until UNL or baseline. Resume at same dose schedule; see guidelines for management in Appendix 5.
Grade 4	Off protocol therapy

For Grade 2 or greater, consider renal biopsy.

Diarrhea/ Colitis	Management/Next Dose for Nivolumab
$\leq$ Grade 1	No change in dose; see guidelines for management in Appendix 5.
Grade 2	Hold until Grade 0 or baseline; see guidelines for management in Appendix 5.
Grade 3	Off protocol therapy; see guidelines for management in Appendix 5.
Grade 4	Off protocol therapy; see guidelines for management in Appendix 5.
See GI AE Algorithm for management of symptomatic colitis (in IB).	
Patients with grade 2 symptoms but normal colonoscopy and biopsies may be retreated after resolution.	
Patients with persistent symptoms greater than 14 days who require steroids should be taken off study treatment.	
Please evaluate pituitary function prior to starting steroids if possible without compromising acute care.	
Evaluation for all patients for additional causes includes C. diff , acute and self-limited infectious and foodborne illness, ischemic bowel, diverticulitis, and IBD.	

Pancreatitis	Management/Next Dose for Nivolumab
Amylase/Lipase	
$\leq$ Grade 1	Hold dose until grade 0.

Grade 2	Hold until Grade 0. Resume at same dose schedule if asymptomatic.
Grade 3	Hold* until Grade 0. Resume at same dose schedule if asymptomatic. Patients who develop symptomatic pancreatitis or DM should be taken off treatment.*
*Grade 4	Off protocol therapy
	Patients may develop symptomatic and radiologic evidence of pancreatitis as well as DM and DKA. Lipase elevation may occur during the period of steroid withdrawal and with other immune-mediated events or associated with colitis, hepatitis, and patients who have asymptomatic lipase elevation typically have self-limited course and may be retreated. For treatment management of symptomatic pancreatitis please follow the Hepatic Adverse Event Management Algorithm (in Appendix 5).
	*Excluding asymptomatic amylase and lipase increases

**Pneumonitis**

≤ Grade 1

**Management/Next Dose for Nivolumab**

Hold dose pending evaluation and resolution to ≤ Grade 0 or baseline including baseline pO2. Resume no change in dose after pulmonary and/or ID consultation.

Grade 2

Hold dose pending evaluation. Resume no change in dose after pulmonary and/or ID consultation if lymphocytic pneumonitis is excluded. Off study if grade 2 symptoms do not improve or worsen after 2 weeks of steroids and dose delay; see guidelines for management in Appendix 5.

Grade 3

Off protocol therapy; see guidelines for management in Appendix 5.

Grade 4

Off protocol therapy; see guidelines for management in Appendix 5.

Distinguishing inflammatory pneumonitis is often a diagnosis of exclusion for patients who do not respond to antibiotics and have no causal organism identified including influenza. Most patients with respiratory failure or hypoxia will be treated with steroids. Bronchoscopy may be required and analysis of lavage fluid for lymphocytic predominance may be helpful. Patients with new lung nodules should be evaluated for sarcoid like granuloma. Please consider recommending seasonal influenza killed vaccine for all patients.

**Other GI N-V**

≤ Grade 1

**Management/Next Dose for Nivolumab**

No change in dose.

Grade 2

Hold pending evaluation for gastritis duodenitis and other immune adverse events or other causes. Resume at same dose schedule after resolution to ≤ Grade 1.

Grade 3

Hold pending evaluation until ≤ Grade 1.

Resume at same dose schedule. If symptoms do not resolve within 7 days

## Grade 4

Patients with grade 2 or 3 N-V should be evaluated for upper GI inflammation and other immune related events.

with symptomatic treatment patients should go off protocol therapy.

Off protocol therapy.

**Fatigue**

≤ Grade 1

Grade 2

Grade 3

**Management/Next Dose for Nivolumab**

No change in dose.

No change in dose.

Hold until ≤ Grade 2. Resume at same dose schedule.

Fatigue is the most common adverse event associated with immune checkpoint therapy. Grade 2 or greater fatigue should be evaluated for associated or underlying organ involvement including pituitary, thyroid, and hepatic, or muscle (CPK) inflammation.

**Neurologic events**

≤ Grade 1

Grade 2

Grade 3

Grade 4

**Management/Next Dose for Nivolumab**

No change in dose.

Hold dose pending evaluation and observation. Hold until ≤ Grade 1; see guidelines for management in Appendix 5. Resume at same dose schedule for peripheral isolated n. VII (Bell's palsy); see guidelines for management in Appendix 5.

Off protocol therapy; see guidelines for management in Appendix 5.

Off protocol therapy; see guidelines for management in Appendix 5.

\*Patients with any CNS events including aseptic meningitis, encephalitis, or myopathy, peripheral demyelinating neuropathy, cranial neuropathy (other than peripheral n. VII), GB syndrome, myasthenia gravis should be off study.

**Endocrine Hypophysitis Adrenal Insufficiency**

Discontinue protocol therapy for grade 4 hypophysitis and grade 3 or greater adrenal insufficiency. Note that protocol-specific actions and management are not strictly by CTCAE grade; see guidelines for management in Appendix 5 for recommendations on I-O therapy and management of adverse events.

**Management/Next Dose for Nivolumab****Fever**

≤ Grade 1

Grade 2

Grade 3

Grade 4

**Management/Next Dose for Nivolumab**

Hold until ≤ Grade 1. Resume at same dose schedule.

Hold until ≤ Grade 1. Resume at same dose schedule.

Hold until ≤ Grade 1. Resume at same dose schedule.

Off treatment

Patients with fever should be evaluated as clinically appropriate. Patients may experience isolated fever during infusion reactions or up to several days after infusion. Evaluation over the course of 1-2 weeks should be done for other autoimmune events that may present as fever. See detailed section below with instructions for management of infusion reactions.

**ALL OTHER EVENTS**

≤ Grade 1

Grade 2

Grade 3

Grade 4

**Management/Next Dose for Nivolumab**

No change in dose

Hold until ≤ Grade 1 OR baseline.\*\* When resolved or following steroids, resume at same dose schedule.

Any grade 2 or 3 drug-related uveitis or eye pain or blurred vision that does not respond to topical therapy and does not improve to Grade 1 severity within the re-treatment period OR requires systemic treatment requires treatment discontinuation.

Any other immune-related grade 3 toxicity not covered in the tables above would require that the patient go off protocol therapy with the following exceptions:

- Any grade 3 or 4 drug-related laboratory abnormality or electrolyte abnormality, not associated with underlying organ pathology, that does not require treatment except for electrolyte replacement OR hormone/steroid replacement **does not** require treatment discontinuation.

Off protocol therapy (except for drug-related laboratory abnormality or electrolyte abnormality, not associated with underlying organ pathology, that does not require treatment except for electrolyte replacement OR hormone/steroid replacement does not require treatment discontinuation).

\*\* Immunologically mediated

**Criteria to Resume Nivolumab**

Patients may resume treatment with nivolumab when the drug-related AE(s) resolve to the grade specified in the tables above and as detailed in Appendix 5.

If the criteria to resume treatment are met, the patient should restart treatment at the next scheduled time point (two-week interval) per the protocol.

**Discontinuation Criteria**

Treatment with nivolumab should be permanently discontinued as specified in the tables above and guidelines for management in Appendix 5. Additional criteria for discontinuation include:

- Any Grade 2 drug-related uveitis or eye pain or blurred vision that does not respond to topical therapy and does not improve to Grade 1 severity within the re-treatment period OR requires systemic treatment;
- Grade 3 drug-related uveitis, pneumonitis, bronchospasm, diarrhea, colitis, neurologic adverse event, hypersensitivity reaction, or infusion reaction of any duration requires discontinuation;
- Grade 3 drug-related thrombocytopenia > 7 days or associated with bleeding requires discontinuation;
- Any Grade 4 drug-related adverse event or laboratory abnormality, with the exception of those noted below:
  - Isolated Grade 4 amylase or lipase abnormalities that are not associated with symptoms or clinical manifestations of pancreatitis and decrease to < Grade 4 within 1 week of onset;
  - Isolated Grade 4 electrolyte imbalances/abnormalities that are not associated with clinical sequelae and are corrected with supplementation/appropriate management within 72 hours of their onset.
  - Any grade 3 or 4 drug-related laboratory abnormality or electrolyte abnormality not associated with underlying organ pathology that does not require treatment except for electrolyte replacement OR hormone/steroid replacement **does not** require treatment discontinuation.
- Any adverse event, laboratory abnormality, or intercurrent illness which, in the judgment of the Investigator, presents a substantial clinical risk to the patient with continued nivolumab dosing;
- A delay in nivolumab treatment of 28 days.

### **Treatment of Nivolumab-Related Infusion Reactions**

Since nivolumab contains only human immunoglobulin protein sequences, it is unlikely to be immunogenic and induce infusion or hypersensitivity reactions. However, if such a reaction were to occur, it might manifest with fever, chills, rigors, headache, rash, pruritis, arthralgias, hypo- or hypertension, bronchospasm, or other symptoms.

All Grade 3 or 4 infusion reactions should be reported as an SAE if criteria are met. Infusion reactions should be graded according to CTCAE v5.0 guidelines.

Treatment recommendations are provided below and may be modified based on local treatment standards and guidelines as appropriate:

**For Grade 1 symptoms** (Mild reaction; infusion interruption not indicated; intervention not indicated): Remain at bedside and monitor patient until recovery from symptoms. The following prophylactic premedications are recommended for future infusions: diphenhydramine 50 mg (or equivalent) and/or acetaminophen 325 to 1000 mg at least 30 minutes before additional nivolumab administrations.

**For Grade 2 symptoms** (Moderate reaction requires therapy or infusion interruption but

responds promptly to symptomatic treatment [e.g. antihistamines, non-steroidal anti-inflammatory drugs, narcotics, corticosteroids, bronchodilators, IV fluids]; prophylactic medications indicated for 24 hours): Stop the nivolumab infusion, begin an IV infusion of normal saline, and treat the patient with diphenhydramine 50 mg IV (or equivalent) and/or acetaminophen 325 to 1000 mg; remain at bedside and monitor patient until resolution of symptoms. Corticosteroid or bronchodilator therapy may also be administered as appropriate. If the infusion is interrupted, then restart the infusion at 50% of the original infusion rate when symptoms resolve; if no further complications ensue after 30 minutes, the rate may be increased to 100% of the original infusion rate. Monitor patient closely. If symptoms recur then no further nivolumab will be administered at that visit. Administer diphenhydramine 50 mg IV, and remain at bedside and monitor the patient until resolution of symptoms. The amount of study drug infused must be recorded on the electronic case report form (eCRF). The following prophylactic premedications are recommended for future infusions: diphenhydramine 50 mg (or equivalent) and/or acetaminophen 325 to 1000 mg should be administered at least 30 minutes before additional nivolumab administrations. If necessary, corticosteroids (recommended dose: up to 25 mg of IV hydrocortisone or equivalent) may be used.

**For Grade 3 or Grade 4 symptoms** (Severe reaction, Grade 3: prolonged [ie, not rapidly responsive to symptomatic medication and/or brief interruption of infusion]; recurrence of symptoms following initial improvement; hospitalization indicated for other clinical sequelae [eg, renal impairment, pulmonary infiltrates]). Grade 4: (life threatening; pressor or ventilatory support indicated): Immediately discontinue infusion of nivolumab. Begin an IV infusion of normal saline, and treat the patient as follows. Recommend bronchodilators, epinephrine 0.2 to 1 mg of a 1:1,000 solution for subcutaneous administration or 0.1 to 0.25 mg of a 1:10,000 solution injected slowly for IV administration, and/or diphenhydramine 50 mg IV with methylprednisolone 100 mg IV (or equivalent), as needed. Patient should be monitored until the investigator is comfortable that the symptoms will not recur. Nivolumab will be permanently discontinued. Investigators should follow their institutional guidelines for the treatment of anaphylaxis. Remain at bedside and monitor patient until recovery from symptoms. In the case of late-occurring hypersensitivity symptoms (eg, appearance of a localized or generalized pruritis within 1 week after treatment), symptomatic treatment may be given (eg, oral antihistamine, or corticosteroids).

### 5.2.2 Cisplatin (CDDP) Dose Modifications During Concurrent Radiation

Patients will be examined and graded for subjective/objective evidence of developing toxicity weekly according to CTCAE v5.0 while receiving concurrent cisplatin with radiotherapy.

Treatment interruptions are allowed if there is symptomatic mucositis or skin reaction that, in the judgment of the clinician, warrants a break. For chemotherapy attributable AEs requiring a break in treatment, resumption of concurrent CDDP may begin when AEs have recovered to the levels specified below. If an AE does not resolve to the levels specified in the sections below prior to the calendar week of the last radiation treatment, treatment off protocol can continue according to the judgment of the treating physician.

There will be no dose re-escalation for concurrent cisplatin. If a patient requires >2 dose reductions then the patient should discontinue protocol therapy. For Grade 4 toxicity, protocol therapy is discontinued. If dosing with study drug is interrupted for > 28 consecutive days due to toxicity, protocol therapy should be discontinued unless otherwise agreed between the

investigators before reintroduction of study drug.

Chemotherapy dosage modifications are based upon lab values obtained within the 24 hours prior to cisplatin and interim non-hematologic toxicities during the week prior to a particular cisplatin dose.

The dose modifications for cisplatin (below) are intended to be permanent (i.e., if the patient's dose is reduced to dose level -1, it remains at the reduced dose level) unless adverse events (AEs) are ongoing requiring further reduction.

#### Cisplatin Dose Modifications for Hematologic Adverse Events during Concurrent Radiation

Starting Dose	Dose Level -1	Dose Level -2
40 mg/m 	30 mg/m 	23 mg/m 

Chemotherapy must not be administered until the ANC is  $\geq$  1,000 and platelets are  $\geq$  75,000. If not, delay 7 days. Cisplatin should be held every week until the above ANC and platelet parameters are met. Dose reductions when cisplatin is resumed after delay for low ANC or platelets will be as follows, based upon counts at time cisplatin was held.

ANC		Platelets	Reduction
$\geq 1000 \text{ mm}^3$	and	$\geq 75,000$	None
$< 1000 \text{ mm}^3$	or	$< 75,000$	One dose level

**Note: Hematologic growth factors for neutropenia or anemia are not allowed during concurrent cisplatin and radiation treatment.**

#### Cisplatin Dose Modifications for Non-Hematologic Adverse Events during Concurrent Radiation

**Neutropenic Fever:** If on the day of scheduled treatment with cisplatin the absolute neutrophil count (ANC) is  $< 1200$ , hold treatment until ANC  $\geq 1200$ , then treat at 100% dose. Neutropenic fever will require permanent 25% dose reduction. Febrile neutropenia is fever of unknown origin without clinically or microbiologically documented infection; ANC  $< 1.0 \times 10^9 \text{ L}$ , fever  $> 38.5^\circ\text{C}$ .

**Thrombocytopenia:** If on the day of scheduled treatment with cisplatin the platelet count is  $< 75,000$ , hold treatment until platelets are  $> 75,000$ , then treat at 100% dose. Thrombocytopenia that results in bleeding will require a 25% dose reduction.

**Renal Adverse Events:** Cisplatin should be administered on the scheduled day of treatment using the following guidelines:

**Note:** If creatinine is > 1.2 mg/dl, clearance must be done in order to make dose adjustment. If the calculated nomogram is 50 mL/min or above, a 24-hour urine collection is not needed, but if the nomogram calculation is less than 50 mL/min, a 24-hour urine collection is mandated.

Once the creatinine has met the above parameters, cisplatin may be restarted with the modifications below, based on the creatinine at the time the cisplatin was held: In general, cisplatin should be held for weekly intervals (rather than restarting cisplatin later in the same week that a dose limiting AE is seen).

Cisplatin dose modifications for creatinine during concurrent radiation			
Creatinine (mg/dL)		Creatinine clearance, measured or calculated ml/min	Cisplatin dose reduction
≤ 1.2	or	> 50	100%
> 1.2	and	40-50	50%
		< 40	Discontinue drug

**Neurologic (neuropathy) adverse events:** If any signs of grade 3 or greater neurotoxicity occur, discontinue cisplatin.

Grade (CTCAE v5.0)	Dose Reduction
0-1	None
2	One dose level
3-4	Discontinue drug

**Ototoxicity:** For new clinical hearing loss not requiring a hearing aid or for tinnitus that interferes with activities of daily living, treat at 50% dose reduction. For hearing loss requiring a hearing aid, discontinue cisplatin. Continue radiation. If the physician is unsure about the severity of the hearing loss, an audiogram is encouraged.

**All Other Non-Hematologic Adverse Events Attributable to Cisplatin during Concurrent Radiation:** For all other non-hematologic adverse events in which toxicity is ≥ grade 2 (CTCAE v5.0), investigators are advised to evaluate and manage correctable issues promptly to prevent worsening of toxicity. For these events in which toxicity is ≥ grade 3, investigators should hold cisplatin, with weekly re-evaluation until AE grade falls to 0-1, then restart cisplatin at one lower dose level.

Note: Grade 3 mucositis is commonly experienced by head and neck cancer patients; the investigator generally would not hold the cisplatin dosing in this case, unless there is unusual concern for progression to grade 4 mucositis. Grade 4 mucositis will require a cisplatin dose reduction.

If a weight change of  $\geq 10\%$  occurs, the cisplatin dose should be adjusted.

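### Section 5.2.2 gives two different cisplatin restart doses and two ANC hold thresholds after low counts, so the count of reductions that decides removal from protocol therapy depends on which rule a site follows

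*Combined protocol and SAP*

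**What the plan says.** Three parts of section 5.2.2 bear on this.

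- **Opening text of 5.2.2.** Reductions are permanent: "There will be no dose re-escalation for concurrent cisplatin". They are also limited in number: "If a patient requires >2 dose reductions then the patient should discontinue protocol therapy".
- **Hematologic subsection.** The ladder is 40, 30 and 23 mg/m². "Chemotherapy must not be administered until the ANC is" at least 1,000 with platelets at least 75,000; otherwise treatment waits in 7-day steps. On restart, "Dose reductions when cisplatin is resumed after delay for low ANC or platelets will be as follows", judged by the counts when the drug was held. The table gives no reduction at or above both limits, and "One dose level" below either.
- **Non-hematologic subsection.** Despite its title, this also has count rules. Under a neutropenic fever label it holds for a treatment-day ANC below 1,200 until it reaches 1,200, "then treat at 100% dose. Neutropenic fever will require permanent 25% dose reduction". Under thrombocytopenia it holds for platelets below 75,000 until they exceed 75,000, "then treat at 100% dose. Thrombocytopenia that results in bleeding will require a 25% dose reduction".

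The non-hematologic subsection also has 50% steps for reduced creatinine clearance and for some hearing changes, and a one-level step for grade 2 neuropathy. None of these parts says which count rule prevails.

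**The concern.** Two rules share a trigger and give different restart doses. Sites in a multicenter trial could treat the same blood count differently, each complying with one part of the section. That is a patient-safety matter in itself.

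The consequence goes beyond a single dose, because the protocol counts reductions and attaches removal from protocol therapy to the count. If two sites count differently, patients with the same history can be handled differently. The primary endpoint is completion of all post-chemoradiation nivolumab (section 8.4.2), so it matters whether protocol therapy here includes nivolumab. Section 5.2.2 does not say.

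**Working it through.** No figure in the plan needs reproducing. The check sets the rules side by side and then counts reductions under each.

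**Step 1. The rules side by side.**

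| Treatment-day finding | Hematologic table | Non-hematologic subsection |
|---|---|---|
| Platelets <75,000, no bleeding | Hold to ≥75,000; restart one level lower | Hold to >75,000; restart at 100% |
| Platelets <75,000, bleeding | Restart one level lower | 25% reduction |
| ANC <1,000, no fever | Hold to ≥1,000; restart one level lower | Hold to ≥1,200; restart at 100% |
| ANC <1,000, neutropenic fever | Restart one level lower | Permanent 25% reduction |
| ANC 1,000 to 1,199, platelets adequate | May be given, no reduction | Hold to ≥1,200; restart at 100% |

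**Step 2. Is one dose level the same as 100%?** The ladder moves in steps of about 25%: 40 × 0.75 = 30, and 30 × 0.75 = 22.5 (listed as 23). One level down therefore roughly matches the 25% reductions for fever and bleeding, and those rows agree in size. It cannot match a 100% restart. The restart conflict is confined to uncomplicated low counts: platelets <75,000 without bleeding, and ANC <1,000 without fever.

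**Step 3. Reductions by number of separate hold-and-resume episodes** (uncomplicated platelets <75,000, starting at 40 mg/m²).

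| Episodes | Hematologic table | Non-hematologic subsection |
|---|---|---|
| 1 | 1 reduction, 30 mg/m² | 0 reductions, 40 mg/m² |
| 2 | 2 reductions, 23 mg/m² | 0 reductions, 40 mg/m² |
| 3 | 3 reductions, over the limit of 2 | 0 reductions, 40 mg/m² |

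The unit is the episode, not the week. The table reduces on resumption after a delay, so several consecutive weekly holds make one delay and one reduction.

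**Step 4. How quickly can the limit be passed on counts alone?** The schemas in section 3.2 show seven weekly cisplatin doses, and each hold lasts at least 7 days. With a dose in radiation week 1, the fastest path is hold in week 2, resume in 3, hold in 4, resume in 5, hold in 6, resume in 7. The third reduction then falls at the last planned dose. The limit can be reached sooner in combination: grade 2 neuropathy and other non-hematologic events of grade 3 or higher also cost a level, so one low-count episode can supply the deciding third reduction.

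**Step 5. The percentage steps.** From the starting dose, 0.50 × 40 = 20 mg/m², below the lowest listed level of 23 mg/m². The text does not say whether such a step counts as one reduction, as more than one, or as exhausting the ladder.

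**The case against.** **Does something elsewhere settle it?** The local-guideline allowance in section 5.1.1.2 concerns how cisplatin is given, such as hydration and antiemetics, and its general reference to institutional practice claims no precedence over the explicit rules of 5.2.2. Section 5.3 adjusts the dose to the organ system with the worst toxicity; it does not choose between two rules for one platelet count. Reading 100% as the full dose of the level in use does not help, because the table still requires a step down.

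**Is the ANC text limited to fever cases?** Its label suggests so, and its scope is unclear. But its trigger is the count on the treatment day. If it applied only to fever, its 100% restart would clash with the permanent 25% reduction in the next sentence.

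**Stronger readings that the documents do not support.**

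- *A patient at ANC 1,100 is ordered to be both treated and held.* The hematologic rule sets a floor for giving the drug; it does not order treatment above it. Holding to 1,200 satisfies both, and both then restart without reduction. The thresholds differ, but this is not a pair of opposed orders.
- *Three weekly holds end protocol therapy.* Three separate episodes are needed (steps 3 and 4), so the route through counts alone is narrow.
- *20 versus 23 mg/m² is a dosing contradiction.* The 50% steps are organ-specific rules separate from the ladder. The gap is in how they are counted.
- *Passing the limit is failure on the primary endpoint.* The nivolumab tables use going off protocol therapy for stopping nivolumab, and where only cisplatin stops, 5.2.2 names the drug, so the inference is reasonable. But 5.2.2 does not say that adjuvant nivolumab stops, the removal rule is worded as a should, and section 5.5.1 allows a switch to carboplatin for unacceptable cisplatin toxicity after consulting the Study Chair.
- *Power falls by a stated amount.* In the 22/40 design of section 8.2.1, exact power is 0.803 at a completion rate of 0.70 and 0.567 at 0.65. The second value assumes that 2 of 40 completers are lost (0.70 − 2/40 = 0.65). The documents give no rate of low-count holds, so neither that number nor any other can be supported.

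**Conclusion.** The contradiction is on the page and nothing in the documents resolves it. It is firmest for platelets below 75,000 without bleeding, where trigger and population are the same and only the restart dose differs. For ANC below 1,000 without fever it holds on a plain reading. The ANC hold thresholds are also inconsistent (1,000 versus 1,200).

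Its size, from a 40 mg/m² start, is 30 versus 40 mg/m² after one episode and 23 versus 40 after two. Each episode adds one reduction or none toward a limit of two. The counting of the 50% steps is a separate ambiguity about the same limit.

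An effect on the primary completion endpoint is possible only if protocol therapy in 5.2.2 includes nivolumab, which is not stated. No power loss is claimed. This is an inconsistency of wording, not a flaw in the statistical design. No view is taken on which threshold or dose is right.

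**What to change.** The sponsor should reconcile the opening text of 5.2.2 and its hematologic and non-hematologic subsections so that:

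1. ANC and platelets each have a single hold threshold and a single restart rule, stated in one place, with the scope of the neutropenic fever paragraph made explicit.
2. The text says which modifications count toward the limit of two reductions, including the 25% and 50% steps, and how a dose below the lowest listed level is counted.
3. The text says whether exceeding the limit ends nivolumab or only cisplatin, and therefore how such a patient is classified for the completion endpoint.

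The choice of thresholds and doses belongs to the sponsor and its clinical investigators. The cost is a wording amendment under section 9.4; sample size, decision boundaries and data collection do not change.
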